Full study protocol and statistical analysis plan

Official Title of the study:

Umbilical cord and maternal blood concentrations of melatonin, soluble urokinase-type plasminogen activator receptor, and orosomucoid 2 in pregnancy complicated by preterm premature rupture of the membranes and histological chorioamnionitis

Date of the document:

October 2020.

Contents:

1. Participant Flow
2. Baseline Characteristics
3. Outcome Measures
4. Endpoints of the study
5. Limitations and Strengths
6. Certain Agreements
7. Results Point of Contact

1. Participant Flow

Recruitment Details

This observational case-control study will be conducted at the Department of Obstetrics and Gynecology, Cengiz Gokcek Public Hospital, Gaziantep, Turkey, between October 2020 and October 2021. The protocol was approved by the Ethics Committee for Clinical Research of Gaziantep University (reference no: 2020/276). The study strictly will be adhered to the principles of the Declaration of Helsinki. All subjects will be included in the study gave oral and written informed consent. 88 women were enrolled in the study in two groups.

Pre-assignment Details

The authors first will be assessed the recruited people to ensure meeting the inclusion and exclusion criteria. The inclusion criteria will be made according to the official documents.

Arm/Group Information *

There are two groups in the study.

Arm/Group Title *

preterm premature rupture of membranes group

Control group

2. Baseline Characteristics

To detect significant difference between groups according to lead levels with a moderate effect size (Cohen's $d=1$), minimum required sample size was estimated as 44 for each group ($\alpha=0.05$, $1-\beta=0.80$). Power analysis was performed by using G power package version 3.1. Kolmogorov Smirnov and Shapiro Wilk tests will be used to test the normal distribution of data. For comparing groups (PPROM/control) the student t-test will be used for variables that have a normal distribution, and the Mann Whitney U test will be used for variables that have not a normal distribution. The ROC analysis will be applied for the determination of cut-off point for variables. Moreover, Spearman correlation test will be used for the relationship of between variables. SPSS for Windows 22.0 and Medcalc programs will be used for statistical analysis. $p<0.05$ will be accepted as statistical significance.

3. Outcome Measures

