Primary Outcome Measures: melatonin, soluble urokinase-type plasminogen activator receptor, and orosomucoid 2 concentrations

Secondary Outcome Measures: composite neonatal outcome (infant weight at delivery, neonatal intensive care unit hospitalization, and APGAR scores etc.)

Tertiary Outcome Measures: obstetric ultrasound examination and fetal-maternal assessment

4. Endpoints of the study:

The primary outcome in these analyses will compare maternal serum melatonin, soluble urokinase-type plasminogen activator receptor, and orosomucoid 2 measurements levels in study group and control group.

5. Limitations and strengths:

There will strengths of this study. The women participating in the study will recruit not received any treatment for PPRM at admission.

6. Certain Agreements

The authors declare that they have no conflict of interest.

7. Results Point of Contact

Corresponding Author: [name], Department of Obstetrics and Gynecology, Cengiz Gokcek Women's and Children's Hospital, Gaziantep, Turkey, [contact]

Address: [name]

GSM: [contact]

[contact]

[contact]

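### Maternal melatonin, a primary marker, is compared between non-randomised groups with no recording, balancing or adjustment for the clock time of the draw

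*Combined protocol and SAP*

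**What the plan says.** All references are to the combined protocol and SAP.

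- Section 3 (Outcome Measures) puts melatonin first of three primary markers: "Primary Outcome Measures: melatonin, soluble urokinase-type plasminogen activator receptor, and orosomucoid 2 concentrations".
- Section 4 (Endpoints of the study) makes the maternal serum level the primary comparison: it "will compare maternal serum melatonin, soluble urokinase-type plasminogen activator receptor, and orosomucoid 2 measurements levels in study group and control group".
- Section 2 (Baseline Characteristics) gives the test: "For comparing groups (PPROM/control) the student t-test will be used for variables that have a normal distribution", with Mann-Whitney otherwise. It names no covariate.
- Section 1 (Participant Flow) describes an observational case-control design. It mentions neither randomisation nor matching.
- Section 5 (Limitations and strengths) has the only phrase that touches on timing: participants "will recruit not received any treatment for PPRM at admission". That describes absence of treatment. It does not say when blood is drawn in either group.

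No section gives a sampling hour, a sampling window, a field for draw time, or a rule for choosing when controls are bled.

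**The concern.** Melatonin is higher at night than by day. This is a general property of the marker and is not stated in the documents. When the hour of the draw is left open, two separate things can go wrong.

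1. **Noise.** Even if both groups have the same mix of hours, the rhythm widens the spread within each group and the test loses power.
2. **Bias.** If the mix of hours differs between groups, part of any difference is a time-of-day effect. It can produce a false positive or mask a real difference. Nothing in a non-randomised design prevents this unless the protocol does.

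An analyst can adjust for the hour only if it was recorded at collection, so the matter has to be settled in the protocol and not left to the analysis.

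**Working it through.** **1. The plan's own figure.** Section 2 sizes the study "with a moderate effect size (Cohen's $d=1$), minimum required sample size was estimated as 44 for each group", at alpha 0.05 and power 0.80. The normal approximation gives n = 2 × (1.96 + 0.842)² / 1² = 15.7, so 16 per group; the exact two-sided t calculation gives 17. One-sided gives 13 or 14, and allowing for Mann-Whitney gives 18 to 20. The stated 44 is not reproduced. With 44 per group, power at d=1 is 99.6%, and 80% power is reached at d=0.604. That mismatch is a separate matter. Both effect sizes are carried forward: d=1 is the plan's figure, and d=0.604 is what 44 per group supports, not a figure in the plan.

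**2. Assumptions, none from the documents.** Night/day ratio R of 2 to 10; SD of log melatonin at a fixed hour of 0.5 to 0.8; 33% of PPROM draws at night; a single day/night step.

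**3. Noise, draw times balanced.** Let k be the clock-time SD divided by the fixed-hour SD. Then d_eff = d / √(1 + k²). For a step, k = (ln R / SD) × √(0.33 × 0.67) = 0.470 × ln R / SD. This gives k of 0.41-0.65 at R=2, 0.65-1.03 at R=3, 0.95-1.51 at R=5 and 1.35-2.17 at R=10.

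Power of the t-test at 44 per group:

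| k | d=1 | d=0.604 |
|---|---|---|
| 0 | 99.6% | 80% |
| 0.5 | 98.6% | 70.7% |
| 1 | 90.6% | 50.8% |
| 1.5 | 73.0% | 34.3% |
| 2 | 54.5% | 24.0% |

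At d=1, power reaches 80% when d_eff = 0.604, that is at k = √(1/0.604² − 1) = 1.32.

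Mann-Whitney power from direct simulation of the step (at least 2,000 datasets per scenario, 33% v 33% at night):

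| R | d=1 | d=0.604 |
|---|---|---|
| 2 | 96-99% | 61-72% |
| 3 | 87-98% | 44-64% |
| 5 | 73-90% | 35-53% |
| 10 | 66-79% | 31-40% |

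Ranges run over SD 0.5 to 0.8. When the step is large and the SD small, Mann-Whitney loses less than the t-test formula implies.

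**4. Bias, draw times hypothetically unbalanced.** The spurious shift on the log scale is (difference in night share) × ln R. For 33% v 5% it is 0.28 × 0.693 = 0.194 at R=2, or 0.24-0.39 SD. At R=10 it is 0.28 × 2.303 = 0.645, or 0.81-1.29 SD, which is the size of the effect the plan wants to detect. Mann-Whitney false-positive rates with no true difference:

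| Night share, PPROM v control | Rate |
|---|---|
| 33% v 33% | near 5% at every R |
| 33% v 15% | about 9-30% over R=2 to 10 |
| 33% v 5% | 17-34% (R=2), 32-51% (R=3), 48-61% (R=5), 58-63% (R=10) |

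If PPROM levels were truly lower by d=1 with the 33% v 5% split, power would be about 70-90% at R=2 and 8-18% at R=10. With a smooth rhythm in place of a step, the inflation at 33% v 5% is smaller, about 10-48%.

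**5. Adjusted model.** A linear model of log melatonin on group plus a night indicator keeps type I error at 4-6% in all these cases. Sine and cosine terms do the same under a smooth rhythm. At d=0.604 its power is 78-81% when balanced and about 71-77% at 33% v 5%. The loss is collinearity: the squared correlation of group with night is 0.25 × 0.28² / (0.19 × 0.81) = 0.127, so d_eff = 0.604 × √0.873 = 0.564.

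**The case against.** **At the plan's effect size there is a large margin.** This stands. At d=1 with balanced draw times, power stays at about 87% or more for R of 2 or 3, and falls below 80% only under a larger assumed rhythm. A reader might infer that the melatonin test is badly underpowered as designed; the documents do not support that. The margin is only partial comfort, however, because section 2 ties the d=1 calculation to another quantity: "To detect significant difference between groups according to lead levels". Lead is not a study marker.

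**The imbalance is conjecture.** This also stands. It is tempting to picture women with PPROM bled on arrival at any hour and controls bled at scheduled hours, and to conclude that a false difference is likely. The documents say neither. Section 5 speaks of treatment status at admission, and nothing describes how or when controls are sampled. The false-positive figures are therefore conditional.

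**The rhythm's size is an outside assumption.** True. Results run from trivial to severe across the assumed range, so no single figure can be attributed to this study.

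**The adjusted model was tested on data that suit it.** Partly met. It was checked under both a step and a smooth rhythm, but not with a misplaced day/night boundary.

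**Cord blood.** A reader might extend the point to a primary cord comparison because the title mentions cord blood. Section 4 limits the primary comparison to maternal serum, and no separate cord calculation was made.

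None of this answers the omission itself: the hour is neither controlled nor recorded, and the test cannot use it.

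**Conclusion.** The point holds as a design weakness that should be corrected. A primary marker with a day-night rhythm is compared between non-randomised groups by an unadjusted test, with nothing in the plan to fix, record, balance or adjust for clock time.

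The size depends on assumptions the documents cannot settle. With balanced hours the harm is lost power only: slight at d=1 for a small rhythm, material for a large one, and substantial at d=0.604 throughout. A false or masked difference needs hours that differ between the groups, which is possible but not shown. Confidence is medium for that reason. The point concerns melatonin only; the other two markers were not examined.

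**What to change.** - In sections 3 and 4, state that the clock time of every maternal draw is recorded, and that control draws are taken in the same clock bands as PPROM draws where practicable.
- In section 2, replace the unadjusted test for melatonin with a linear model on log melatonin, with group plus clock time (a day/night indicator, or sine and cosine terms) as the primary comparison.
- If cord melatonin is analysed, record the time of birth and apply the same model as a secondary analysis.
- Section 1 already reports 88 women as enrolled. If samples are in hand, recover the draw times from hospital records where these hold them.

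**Cost.** One field on the sample form, attention to the hour at which controls are bled, and one or two degrees of freedom. No extra participants or assays are needed. Strict night-time matching of controls would be a heavier burden, hence the wording on practicability. If hours differ strongly by group, some power is lost to collinearity: about 71-77% in place of 80% at d=0.604 with 33% v 5%.
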